9.1.2 Evaluation of New Lesions

The appearance of new lesions will not be considered Progressive Disease (PD). The goal of this study is to evaluate the safety and efficacy of stereotactic radiotherapy to individual lesions. If subject develops new lesions, this would not impact the study results. For example, a new lesion might be amenable to SBRT. However, on this protocol such new lesions will not be treated.

9.1.4 Evaluation of Best Overall Response

The best overall response is the best response recorded from the start of the treatment until disease progression/recurrence (taking as reference for progressive disease the smallest measurements recorded since the treatment started). The patient's best response assignment will depend on the achievement of both measurement and confirmation criteria.

For Patients with Measurable Disease (i.e., Target Disease)

DF/HCC Protocol #:15-278 Protocol Version Date 02/07/2019

Target Lesions	New Lesions	Best Overall Response	Remarks
CR	Yes or No	CR	
PR	Yes or No	PR	
SD	Yes or No	SD	Documented at least once ≥6 wks. from study entry
PD	Yes or No	PD	No prior SD, PR or CR

Study Calendar

	Pre- study	Week 1	Week 2	One month (+/- 2 wks) post SBRT	Every 3 months (+/- 2 wks) after first assessment done 6weeks after SBRT during first year	Every 6 months (+/- 6 wks) during second year	Annually for the third, fourth, and fifth years
SBRT		X	X				
Informed	X						
consent							
History	X			X	X	X	X
Physical Exam	X	X	X	X	X	X	X
CT chest and	X			x (6	X	X	X
tumor				weeks			
measurement				post SBRT)			
PFTS	X				X ^a		
CBC	X						
Adverse event reporting b		X	X	X	X	X	

^a PFTs (pulmonary function tests) will be performed only at 3 and 6 months (+/- 2 wks) after SBRT.

10. DATA COLLECTION

10.1 Study Documentation

After a participant is enrolled on the study, we will collect information about their diagnosis, treatment, and any side effects of treatment as well as demographic data. Information regarding the tolerability of SBRT in the study population and any information about disease relapse if it should occur after study treatment. Study participants will be assigned a study number by the study team and all information will be de-identified when analyzed. This de-identified data will be stored electronically in the ODQ system and protected by multiple firewalls that exist within the Partners network. Any paper records including Case Report Forms will be stored in an office secured by a lock that only study team members have access to.

Original source documents supporting entries in the case report forms include but are not limited to hospital records, clinical charts, laboratory and pharmacy records, recorded data from automated instruments, microfiches, photographic negatives, microfilm or magnetic media, and/or x-rays.

^b All serious adverse events that occur after the initial dose of study treatment, during treatment, or within 6 months of the last dose of treatment

11 STATISTICAL CONSIDERATIONS

11.1 Study Design/Endpoints

A 3+3 study design will be used in the Phase I portion and patients will enter the study in sets of three for each cohort. For a given dose level, if none of three patients experiences a DLT, this dose level will move forward to the Phase II portion. However, if one patient experiences a DLT among the first three patients at any dose level, three more patients will be treated at that dose level. The dose level will enter the Phase II portion if no further DLT is observed following observation period of 6 months from treatment completion of third patient in the cohort. If a DLT is observed in any of the three additional patients, this dose level will not move forward to the Phase II portion and the dose will be de-escalated to the next lower level. If two or more patients experience a DLT among the first 3 patients, dose de-escalation will ensue, if applicable, without further testing of that dose level in the phase II portion. The table below shows the probability of entering the phase II portion for a dose level under different true DLT rates.

True DLT rate	5%	10%	15%	20%	30%	40%
Probability of entering phase II	0.97	0.91	0.81	0.71	0.49	0.31

Once a dose level enters the Phase II portion, a two-stage design will be used to evaluate efficacy. The first stage will accrue seven patients, including the patients enrolled at the same dose level in the Phase I portion. If at least two responses are observed among the seven patients, additional eight patients will be entered. If five or more responses are observed among the fifteen patients, there will be no further dose escalation and this dose level will be considered tolerable and effective for this patient population. With this design, the Phase II portion has 90% power to test the response rate of 50% vs. 20% based on a 0.14 level one-sided exact binomial test. The probability of stopping early is 0.58 if the true response rate is 20%; whereas if the true response rate is 50%, this probability is 0.06.

If a dose level examined in the Phase II portion does not meet the pre-specified criteria for efficacy, the next higher dose level will start in the Phase I portion until a dose level that meets both Phase I and Phase II criteria for safety and efficacy is found. If a dose level does not meet the safety criteria (none of three or no more than one out of six develops a DLT), and the next lower dose level does not meet the Phase II pre-specified criteria for efficacy, the study will be terminated. If two or more DLTs are observed at the starting dose level, the SBRT dose will be de-escalated to the next lower dose level; if this happens at dose level 1 (the lowest dose level), the study will be terminated. The same Phase I/II design applies to both cohorts, renal tumor (cohort 1) and Ewing patients (cohort 2), separately, except for the starting dose level in the Phase I portion.

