Non-renal tumor dose escalation scheme: Three participants with non-renal tumors will be treated starting at dose level 2. If no dose-limiting toxicities (DLTs, see definitions in 6.2) are seen, that cohort will move on to the phase II portion of the study. If one DLT occurs at the initial dose level, then 3 more patients will be accrued to that cohort. If no further DLTs occur in those 3 patients treated at the initial dose level, then that cohort will move on to the phase II portion of the study. In the phase II portion, if the efficacy criteria are not met, three more patients will be enrolled at the next dose level. Dose will be escalated to the next dose level (3) for the next three patients. If one DLT, an additional three patients will be enrolled at that current dose level. If two or three DLTs, no dose escalation will occur; if this is at the starting dose level 2, dose will be deescalated to the next lower dose level for the next three patients, down to a minimum of dose level 1. If three patients are treated at dose level 2, three more at dose level 3, and there are still no DLTs, the dose will be held at level 3 for all additional non-renal tumor patients.

Renal tumor dose escalation scheme: Three participants with renal tumors will

be treated starting at dose level 1. If no dose-limiting toxicities (DLTs, see definitions in 6.2) are seen, that cohort will move on to the phase II portion of the study. If one DLT occurs at the initial dose level, then 3 more patients will be accrued to that cohort. If no further DLTs occur in those 3 patients treated at the initial dose level, then that cohort will move on to the phase II portion of the study. In the phase II portion, if the efficacy criteria are not met, three more patients will be enrolled at the next dose level. Dose will be escalated to the next dose level (2) for the next three patients. If one DLT, an additional three patients will be enrolled at that current dose level. If two or three DLTs, no dose escalation will occur; if this is at the starting dose level 1 (the lowest dose level), the study will be terminated. If three patients are treated at dose level 2, three more at dose level 3, and there are still no DLTs, the dose will be held at level 3.

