6.1.2.6 Dose-escalation (please refer to Dose Schema section 6.1.2.5): The Phase I and Phase II portions will be done sequentially. If a dose level does not meet the safety criteria (none of three or no more than one out of six develops a DLT), and the next lower dose level does not meet the Phase II pre-specified criteria for efficacy, the study will be terminated. If two or more DLTs are observed at the starting dose level, the SBRT dose will be de-escalated to the next lower dose level; if this happens at dose level 1 (the lowest dose level), the study will be terminated.

The same Phase I/II design applies to both cohorts, Wilms and sarcoma patients, separately, except for the starting dose level in the Phase I portion. There are 3 dose levels (8, 10 and 12 Gy x 3) in this study. Patients with Wilms tumor or other renal tumors will start at dose level 1 (8 Gy x 3) and dose escalation will stop for this cohort at dose level 3 (12 Gy x 3). Ewing sarcoma and rhabdomyosarcoma patients will start at dose level 2 (10 Gy x 3).

6.1.2.7 Stopping rules: If two or more DLTs are observed at the starting dose level, the SBRT dose will be de-escalated to ther next lower dose level; if this happens at dose 1 (the lowest dose level), the study will be terminated.

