6.2 Dose-limiting toxicities (DLTs)

DLTs are toxicities experienced between the start of the stereotactic radiotherapy and 6 months after radiotherapy. DLTs will be graded according to the CTEP active version of the National Cancer Institute's (NCI) Common Terminology Criteria for Adverse Events (CTCAE), located at:

http://ctep.cancer.gov/protocolDevelopment/electronic applications/ctc.htm.

The current version is CTCAE v4.0.

For this study, DLTs are defined as follows: The following grade 2 or higher toxicities:

- Myelitis
- Esophageal fistula, perforation, hemorrhage

The following grade 3 or higher toxicities considered to be a direct result of therapy:

- Pneumonitis
- Pericarditis, pericardial effusion
- Esophageal necrosis, stenosis, ulcer
- Dyspnea

The following grade 4 toxicities:

- Esophagitis
- Pericardial tamponade
- Pulmonary toxicity excluding infectious pneumonia
- Skin toxicity
- Hemoptysis/pulmonary hemorrhage

All grade 5 toxicities, including:

- Pulmonary toxicity including pneumonitis
- Excluding infectious pneumonia

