11.3 Analysis of Primary Endpoints

This is a Phase I/II study to determine the lowest dose level of stereotactic body radiotherapy (SBRT) with an acceptable safety profile and efficacy in patients with relapsed Ewing sarcoma, rhabdomyosarcoma, soft tissue sarcoma or primary renal tumors (including Wilms tumor) who have limited pulmonary metastases. The primary objective of the Phase I portion is to evaluate the toxicity profile of each dose level and determine whether a given dose level could move forward to the Phase II portion. The primary endpoint of the Phase II portion is response to treatment (disease control at 6 weeks in the treatment field). The response rate along with the 95% two-stage confidence interval will be reported by dose level for each cohort. The Phase I and Phase II designs will be employed sequentially, i.e., a dose level will be examined in the Phase I portion for safety and then in the Phase II portion for efficacy if the Phase I safety criteria are met, to achieve the goal of balancing safety and efficacy in these rare tumor populations.

Given that the starting dose in the Phase I portion will be different for the patients with Wilms/renal tumor and the patients with relapsed Ewing sarcoma, rhabdomyosarcoma, soft tissue sarcoma, patients will be enrolled in two distinct cohorts, and escalate through the dose levels and enter the Phase II portion independently.

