12.3 Study Monitoring

The DF/HCC Data and Safety Monitoring Committee (DSMC) will review and monitor toxicity and accrual data from this trial. The committee is composed of clinical specialists with experience in oncology and who have no direct relationship with the study. Information that raises any questions about participant safety will be addressed with the Principal Investigator and study team.

The DSMC will meet quarterly and/or more often if required to review toxicity and accrual data. Information to be provided to the committee may include: up-to-date participant accrual; current dose level information; DLT information; all grade 2 or higher unexpected adverse events that have been reported; summary of all deaths occurring within 30 days for Phase I or II protocols; any response information; audit results, and a summary provided by the study team. Other information (e.g. scans, laboratory values) will be provided upon request. Information that raises any questions about participant safety will be addressed with the Principal Investigator and study team.

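### Section 11.1 calls a dose level tolerable on 5 of 15 responses, so DLTs in the 9 to 12 patients treated after the Phase I gate cannot change that word

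*Combined protocol and SAP*

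**What the plan says.** Section 11.1 runs each dose level through a 3+3 and then a two-stage efficacy test. The level enters Phase II with no DLT in three patients, or one in six. Stage one takes seven patients, including those already treated at that level in Phase I. With at least two responses, eight more are added. With five or more responses in fifteen, "there will be no further dose escalation and this dose level will be considered tolerable and effective for this patient population". That condition counts responses only.

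The safety requirement is given once as a number: "safety criteria (none of three or no more than one out of six develops a DLT". Section 11.3 divides the work in the same way, with each level examined "for safety and then in the Phase II portion for efficacy if the Phase I safety criteria are met".

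A further rule appears in sections 6.1.2.6, 6.1.2.7 and 11.1. In 11.1 it reads: "If two or more DLTs are observed at the starting dose level, the SBRT dose will be de-escalated to the next lower dose level". At level 1 the consequence is termination. Section 6.1.2.7, headed as stopping rules, opens the same way: "If two or more DLTs are observed at the starting dose level". None of the three places names a phase or a denominator. Section 6.1.2.5 gives the same consequence inside the sets of three: "If two or three DLTs, no dose escalation will occur; if this is at the starting dose level 2, dose will be deescalated".

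Section 6.2 sets the window: "DLTs are toxicities experienced between the start of the stereotactic radiotherapy and 6 months after radiotherapy". Response is read at 6 weeks (sections 2.2.2 and 9).

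**The concern.** The trial's main conclusion is a joint claim about safety and efficacy in children. With three Phase I patients, 15 - 3 = 12 of the fifteen are treated after the only DLT test. With six, 15 - 6 = 9 are. Followed to the letter, the plan would call a level tolerable whatever DLTs those patients had, provided five of the fifteen responded. The word would rest on 3 or 6 patients although 15 had been observed. Because response is read at 6 weeks and DLTs accrue for 6 months, the verdict could also be issued before the last patients' DLT windows close.

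The unstated scope of the two-or-more-DLT rule adds a practical difficulty. If a second DLT occurred in, say, the tenth patient at a starting level, the text would not tell the investigator directly whether the rule applied. In cohort 1 at level 1 the consequence would be termination.

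**Working it through.** **Inputs.** The gate and response rules, the 50% and 20% response rates and the DLT rates of 5-40% are all from section 11.1. Assumptions: DLT and response are independent, all Phase I patients are evaluable for response, 15 are treated, and all DLTs are known before the verdict. Let p be the true DLT rate.

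**1. Reproduce the plan's figures.**
- Gate: (1-p)^3 + 3p(1-p)^5. At 5/10/15/20/30/40% this gives 0.973, 0.906, 0.814, 0.709, 0.494 and 0.309, matching the table in 11.1.
- Response rule: sum over x = 2 to 7 of P(Bin(7,r) = x) × P(Bin(8,r) ≥ 5 - x). This gives 0.903 at r = 50% and 0.141 at r = 20% (stated: 90% power, 0.14 level).
- Early stopping: P(Bin(7,r) ≤ 1) = 0.577 at 20% and 0.0625 at 50% (stated: 0.58 and 0.06).

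The plan's arithmetic is right. The gap is in the decision rule.

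**2. Verdict as written, with DLTs tested only in Phase I.** P(declared) = gate × 0.903. At 30%: 0.494 × 0.903 = 0.446.

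**3. Verdict if it also required fewer than k DLTs in 15.** P(gate passed and fewer than k DLTs) = (1-p)^3 × P(Bin(12,p) ≤ k-1) + 3p(1-p)^5 × P(Bin(9,p) ≤ k-2).

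As an illustration take k = 5, since 5/15 = 33% is the same proportion as the 2/6 that fails Phase I. At 30%: 0.343 × 0.724 + 0.151 × 0.730 = 0.359, and 0.359 × 0.903 = 0.324.

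| True DLT rate | Declared, as written | Declared, cut of 5 of 15 | Difference | P(≥5 DLTs, given entry) |
|---|---|---|---|---|
| 5% | 0.879 | 0.879 | 0.000 | 0.000 |
| 10% | 0.818 | 0.814 | 0.004 | 0.005 |
| 20% | 0.640 | 0.591 | 0.049 | 0.076 |
| 30% | 0.446 | 0.324 | 0.12 | 0.275 |
| 40% | 0.279 | 0.126 | 0.15 | 0.548 |

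If the true response rate is well above 50%, the efficacy rule hardly filters. At 90% it is passed almost surely, so at a 30% DLT rate the two probabilities become 0.494 and 0.359.

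**4. What the two-or-more rule would do if it counted all 15.** Put k = 2 in step 3. At 10%: 0.729 × 0.659 + 0.177 × 0.387 = 0.549. The chance of at least two DLTs given entry is 1 - 0.549/0.906 = 0.39, and P(declared) is 0.549 × 0.903 = 0.496. At 5/20/30/40%, the chance of at least two given entry is 0.15, 0.76, 0.93 and 0.98.

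**The case against.** The strongest reply is that the plan means what section 11.3 says: safety is settled in Phase I and efficacy in Phase II. The 5-of-15 rule applies only to a level that has entered Phase II, and 11.1 seeks a level meeting both sets of criteria, so the word tolerable refers to the gate already passed. Carrying a 3+3 result into a small efficacy expansion is a recognised choice. Oversight is also real. The DSMC meets quarterly and may receive "up-to-date participant accrual; current dose level information; DLT information". Serious events reach the PI within 24 hours (6.3.2.3.2), and toxicities are tabulated by dose level (11.4). At 3 to 5 patients a year per cohort (11.2), about one patient per cohort enters between meetings (3/4 = 0.75; 5/4 = 1.25), so each DLT can be reviewed individually.

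Most of this stands. It lowers the urgency, and it rules out any inference that the claim of tolerability has no safety basis or that Phase II toxicity goes unwatched. It does not supply a criterion: none of these safeguards sets a DLT count for the later patients or for the verdict.

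A reader might also infer that the two-or-more rule counts all 15 patients, so that the plan supports two very different Phase II parts. The verdict would then move by 0.879 - 0.749 = 0.13 at a 5% DLT rate and 0.818 - 0.496 = 0.32 at 10%. The documents do not support resting the point on that. Section 6.1.2.5 gives the same consequences within the sets of three, 11.1 does so for the first and additional three, the safety criteria use denominators of 3 and 6 only, and 11.3 ties safety to Phase I. A rule that rejected 39% of entered levels at a 10% DLT rate is also unlikely to be intended. Only the heading of 6.1.2.7 and the missing phase limit favour the wider reading. That justifies a clarifying phrase.

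**Conclusion.** The point holds in a limited form. The final declaration in 11.1 has no DLT condition beyond the Phase I gate, so later DLTs cannot alter it. On the Phase I reading of the two-or-more rule, the effect is negligible at true DLT rates of 5-10%. For context, the adult series in section 1.2 report 0.0-10.1% toxicity of grade 3 or greater, although that is not this trial's DLT definition. It matters from about 20%: at a 50% response rate, a level with a 30% DLT rate is declared tolerable and effective with probability 0.446, against 0.324 with a cut of 5 of 15. The sponsor's own table runs to 40%, where 31% of levels still enter Phase II.

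The figures rest on the assumptions listed with the inputs and on an illustrative cut-off. Severity is minor to moderate and confidence moderate, because the gate and the DSMC give partial protection and the size depends on an unknown DLT rate.

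**What to change.** 1. In 11.1, make the tolerability statement also require that cumulative DLTs among all patients treated at that level, starting or escalated, stay below a pre-specified boundary. Scale it to the number treated, and apply it during Phase II accrual as well as at the end. Not tolerable at 5 or more of 15 is one example of an endpoint; the choice is the sponsor's. Treat a crossing as not meeting the safety criteria.
2. In the same amendment, state in 6.1.2.6, 6.1.2.7 and 11.1 that the two-or-more rule belongs to the Phase I 3+3. Doing this without step 1 would remove the only wording that could be read as a Phase II DLT rule.
3. Issue the final verdict only after the last patient's 6-month DLT window has closed.
4. Extend the DLT table in 11.1 to the end of Phase II under the chosen boundary. The cut of 5 above is a single end-of-study test; stricter earlier looks would lower the declaration probabilities further, so they need their own calculation.

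**Cost.** The change is wording in three sections and extra table rows; the DLT data are already collected. The verdict may come up to about 4.5 months later (6 months less 6 weeks). An active dose is slightly more likely to be rejected: 0.640 falls to 0.591 at a 20% DLT rate with the end-of-study cut. A crossing at level 2 in cohort 2 could mean up to 15 more patients at level 1, about 3 years at 5 a year; on average this is at most 15 × 0.049 = 0.7 extra patients at a 20% DLT rate. A crossing at level 1 in cohort 1 would mean termination, so the sponsor should set the boundary with that in mind.

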7. OTHER THERAPIES

If systemic anti-cancer treatment is urgently required during the two weeks of study treatment, the subject will be removed from the study and replaced. However, patients will be allowed to receive concurrent immunotherapy.

During the Phase I portion, if clinically indicated, systemic therapy can be given and the subject will remain evaluable for the phase I (toxicity) portion. Surgery (other than to index lesions) will be allowed. These patients will be scored as unevaluable for response assessment.

During the Phase II portion, if systemic therapy is needed prior to the 6 week post-treatment assessment time, that subject but will be scored as UNEVALUABLE for response assessment but will be followed for toxicity. Surgery (other than to index lesions) is allowed if clinically indicated and the subject will remain evaluable.

However, if the reason for non-protocol surgery or chemotherapy is disease worsening of the index lesions, those patients would be scored as disease progression

Patients may receive Decadron orally prior to each fraction of radiotherapy per physician discretion.

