9. PARTICIPANT ASSESSMENTS

Evaluation of response. All participants included in the study will be assessed for response to treatment, unless the subject received systemic therapy prior to the 6 week assessment.. Response in this study will be defined as disease control in the treated lesion at 6 weeks. We will continue to assess response and consider best overall response as a secondary objective.

Each participant will be assigned one of the following categories: 1) complete response, 2) partial response, 3) stable disease, 4) progressive disease, 5) early death from malignant disease, 6) early death from toxicity, 7) early death because of other cause, or 9) unknown (not assessable, insufficient data). By arbitrary convention, category 9 usually designates the "unknown" status of any type of data in a clinical database.

Disease control at 6 weeks will include complete response (CR), partial response (PR) and stable disease (SD).

Patients will be seen weekly during treatment for physical examination and assessment of acute side effects. They will then be seen at one month from the end of study treatment for physical examination, A CT at will be done at 6 weeks post completion of SBRT and then every three months with physical examination and CT scan of the chest during the first year, followed by every 6 months for the next year and then annually until year 5, as is considered standard of care. (See: Study Calendar)

The lesion or lesions treated will be measured as well as new lesions identified. Pulmonary function tests will be done at 3 months post treatment, then at 9 months.

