9.1 Response Criteria

9.1.1 Evaluation of Target Lesions (response will be measured using CT scans)

Complete Response (CR)

Disappearance of all target lesions. Any pathological lymph nodes (whether target or non-target) must have reduction in short axis to ≤ 10 mm.

Partial Response (PR)

At least a 30% decrease in the sum of the diameters of target lesions, taking as reference the baseline sum diameters

Progressive Disease (PD)

At least a 20% increase in the sum of the diameters of target lesions, taking as

reference the smallest sum on study (this includes the baseline sum if that is the smallest on study). In addition to the relative increase of 20%, the sum must also demonstrate an absolute increase of at least 5 mm.

NOTE: The appearance of one or more new lesions will not be considered progression.

Stable Disease (SD)

Neither sufficient shrinkage to qualify for PR nor sufficient increase to qualify for PD, taking as reference the smallest sum diameters while on study. (Note: a change of 20% or more that does not increase the sum of the diameters by 5 mm or more is coded as stable disease). To be assigned a status of stable disease, measurements must have met the stable disease criteria at least once after study entry at a minimum interval of 6 weeks.

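### Is a 20% null rate wrong for a Phase II rule that counts stable disease at 6 weeks as response?

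*Combined protocol and SAP*

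**What the plan says.** Section 11.1 runs a two-stage test at each dose level that passes the safety screen. Seven patients come first, including those treated at that level in Phase I. Two or more responses bring in eight more, and five or more responses among the 15 end escalation and label the dose tolerable and effective. The stated properties are "90% power to test the response rate of 50% vs. 20% based on a 0.14 level one-sided exact binomial test", with early-stopping probabilities of 0.58 at a 20% rate and 0.06 at 50%.

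The event being counted is defined elsewhere. Section 9 says: "Disease control at 6 weeks will include complete response (CR), partial response (PR) and stable disease (SD". Section 11.3 names the Phase II endpoint as "response to treatment (disease control at 6 weeks in the treatment field". Section 2.2.2 refers only to RECIST and does not mention stable disease.

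For progression, Section 9.1.1 requires a 20% rise in the sum of diameters and adds that "the sum must also demonstrate an absolute increase of at least 5 mm". Section 9.1.2 adds: "The appearance of new lesions will not be considered Progressive Disease (PD". Section 7 works in the other direction: "if the reason for non-protocol surgery or chemotherapy is disease worsening of the index lesions, those patients would be scored as disease progression". For Phase I patients who receive other treatment, Section 7 says: "These patients will be scored as unevaluable for response assessment". For reporting, Section 11.3 states: "The response rate along with the 95% two-stage confidence interval will be reported by dose level for each cohort".

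**The concern.** A 20% versus 50% contrast looks like one set for tumour shrinkage, yet the rule also counts lesions that merely fail to grow. Read as a disease-control null, 20% says that about 80% of patients on an ineffective dose would lack control at 6 weeks. Nothing in the protocol supports that. The only control rates it gives, 86% to 98% in the table in Section 1.2, come from treated series presented in the context of adult lung cancer, so they say nothing about an ineffective dose.

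The progression rule makes the question sharper, because it needs a double threshold and ignores new lesions. If stable disease at 6 weeks were common without any treatment effect, the true false-go rate would exceed 0.14. Because a go ends escalation, the first safe level could be called effective too easily. Finding the lowest level that is both safe and effective is the trial's stated purpose (Section 2.1).

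**Working it through.** **Inputs (Section 11.1).** Stage 1: 7 patients, continue at 2 or more. Stage 2: 8 more patients, go at 5 or more of 15. Null rate 0.20, target rate 0.50.

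**Formulas.** With true rate p:

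- P(early stop) = (1−p)^7 + 7p(1−p)^6
- P(go) = Σ over x = 2..7 of C(7,x) p^x (1−p)^(7−x) × P(Bin(8,p) ≥ 5−x)

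**Reproducing the plan's figures.**

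- Early stop at 0.20: 0.2097 + 0.3670 = 0.5767 (printed 0.58).
- Early stop at 0.50: 8/128 = 0.0625 (printed 0.06).
- Go at 0.20: x = 2 gives 0.2753 × 0.2031 = 0.0559; x = 3 gives 0.1147 × 0.4967 = 0.0570; x = 4 gives 0.0287 × 0.8322 = 0.0239; x ≥ 5 gives 0.0047. The unrounded total is 0.1414 (printed 0.14).
- Go at 0.50: 0.1404 + 0.2638 + 0.2724 + 0.2266, unrounded total 0.9031 (printed 90%).

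All four agree. A single-stage test at 5 of 15 would give 0.164 and 0.941, so the printed figures are those of the two-stage rule.

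**Sensitivity on both sides of 20%.** Every rate other than the plan's 20% and 50% is an assumption.

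| True control rate | P(go) | P(early stop) |
|---|---|---|
| 10% | 0.01 | 0.85 |
| 15% | 0.05 | 0.72 |
| 20% | 0.14 | 0.58 |
| 25% | 0.27 | 0.44 |
| 30% | 0.43 | 0.33 |
| 40% | 0.72 | 0.16 |
| 50% | 0.90 | 0.06 |

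**Can the documents place the null rate?** The 5 mm condition is the harder one when 20% of the sum of diameters is below 5 mm, that is, below a sum of 25 mm. A single 4 mm lesion must reach 9 mm (+125%) and a single 10 mm lesion must reach 15 mm (+50%). But Section 3.1 allows up to three treated lesions per hemithorax, and the rule applies to the sum. Three 10 mm lesions (sum 30 mm) need only 20%, and six 4 mm lesions (sum 24 mm) need 5/24 = 21%. How demanding the rule is depends on case mix, and no growth rates are given.

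Three features lower the counted rate: early death is a separate category in Section 9, other treatment for index-lesion worsening counts as progression, and unevaluable patients count as failures if they stay in the denominator. For the last, with an assumed unevaluable fraction u, the counted rate is p(1−u). At u = 0.20, control of 25% among evaluable patients counts as 0.25 × 0.80 = 20%, so P(go) is 0.14. At 30% it is 0.25, and at 40% it is 0.50.

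**What a different null would buy.** Two rules at the same 7 + 8 patients:

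- At least 4/7, then 10/15 (50% versus 80%): false-go 0.141, power 0.92. P(go) at a true 60% is 0.38.
- At least 2/7, then 7/15 (30% versus 60%): false-go 0.128, power 0.90. P(go) at a true 60% is 0.90.

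For the same dose with 60% control, the first rejects it 62% of the time and the second 10%. Nothing in the documents chooses between them.

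**Cost.** A level that fails efficacy opens the next one. The non-renal cohort has one level above its start: up to 15 patients, 15/5 = 3 years at the accrual rate in Section 11.2 (that section itself prints 2 years). The renal cohort has two: up to 30 patients, 30/3 = 10 years. Each new level also adds 6 months of toxicity observation.

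**The case for a change.** The strongest case for change rests on steepness and finality. A five-point error in the null, from 20% to 25%, nearly doubles the false-go rate (0.14 to 0.27). A go is a decision and not just a report. It can rest on 5 of 15, an ordinary exact 95% interval of 12% to 62%, which still contains 20%, with ten patients lacking control. The planned interval would show that weakness but would not reopen escalation. Rules with similar error rates exist at the same sample size, and a justification costs only a few sentences.

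Much of this stands. The rationale is missing, Section 2.2.2 is less explicit than Sections 9 and 11.3, and Section 11.1 does not say whether unevaluable patients are replaced or counted as failures.

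What does not stand is the inference that 20% is too low. Any single-arm error rate is conditional on its null, and 20% may simply be the rate the sponsor regards as unacceptable. The sensitivity runs both ways: if the counted rate for an ineffective dose were 15%, the false-go rate would be 0.05. Stricter cut-offs also carry a risk beyond the extra patients. Under Section 11.1, a level that fails efficacy followed by a higher level that fails safety ends the study, so termination without a selected dose becomes more likely. Changing cut-offs after responses at an open level have been seen would add a data-dependence problem of its own.

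**Conclusion.** No change to the plan follows. The operating characteristics are correct at the rates stated, and the endpoint is defined consistently where it is used (Sections 9 and 11.3). What is missing is an explanation of 20% and 50% for disease control. The documents cannot show that these rates are wrong, or in which direction. The possible effect is large, with P(go) running from 0.01 to 0.72 as the assumed rate goes from 10% to 40%, but that is a range over assumptions and not an estimate of error.

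Moving the null is a debatable trade-off. It might guard against stopping too early, but it would reject more doses with intermediate control, could add up to 15 or 30 patients in slowly accruing cohorts, and needs a null that the documents do not supply.

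The smaller gaps can be filled sensibly at analysis. Sections 9 and 11.3 settle that stable disease counts. The response categories are recorded, so CR plus PR can be shown beside disease control. The handling of unevaluable patients can be stated with the result. The two-stage interval will show how weak a bare pass is, best overall response is already a secondary objective, and Section 13 plans a further Phase II protocol if results are favorable. None of these would reverse a stop in escalation, but they limit how much rests on 5 of 15.
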